12.4. Primary Efficacy Analysis

12.4.1. Primary estimand

Table 23: Effect of DSS on proportion of patients initiated on combination therapy, escalation of monotherapy or escalation of combination therapy, regardless of prescriber use of the DSS

Patients with primary outcome at 16 weeks	Trial arm		Adjusted Risk Ratio*	95% confidence interval
	DSS	Control		
N			x.xx	x.xx to x.xx
n (%)				

*adjusted for country, site type (secondary/tertiary care/mix of both) and study site

12.4.2. Supplementary estimand

Table 24: Effect of DSS on proportion of patients initiated on combination therapy, escalation of monotherapy or escalation of combination therapy in patients for whom the prescribing physician used the DSS

Patients with primary outcome at 16 weeks	Trial arm		Adjusted Risk Ratio*	95% confidence interval
	DSS	Control		
N			x.xx	x.xx to x.xx
n (%)				

*adjusted for country, site type (secondary/tertiary care/mix of both) and study site

12.5. Secondary Efficacy Analysis

12.5.1. Time to event outcomes

Table 25: Effect of DSS on time to initiation of LLT combination therapy or escalation of LLT monotherapy or escalation of LLT combination therapy

Patients with primary outcome	Trial arm		Adjusted Hazard Ratio*	95% confidence interval
	DSS	Control		
N			x.xx	x.xx to x.xx
n (%)				
Median survival (weeks) (95% CI)				

*adjusted for country, site type (secondary/tertiary care/mix of both) and study site

12.5.2. Continuous outcomes

Table 26: Effect of DSS on lipid profile at Week 16

Trial arm	DSS	Control	Adjusted mean difference at Week 16*	95% confidence interval
LDL-C level (mmol/L)				
N (missing)			x.xx	x.xx to x.xx
Mean (SD)				
Median (IQR)				
Non-HDL-C level (mmol/L)				
N (missing)			x.xx	x.xx to x.xx
Mean (SD)				
Median (IQR)				
HDL-C level (mmol/L)				
N (missing)			x.xx	x.xx to x.xx
Mean (SD)				
Median (IQR)				
Total cholesterol (mmol/L)				
N (missing)			x.xx	x.xx to x.xx
Mean (SD)				
Median (IQR)				
Triglycerides (mmol/L)				
N (missing)			x.xx	x.xx to x.xx
Mean (SD)				
Median (IQR)				

*adjusted for country, site type (secondary/ tertiary care/mix of both) and study site

12.5.3. Binary outcomes

Table 27: Effect of DSS on proportion of patients receiving LLT combination therapy

Patients receiving LLT combination therapy	Trial arm		Adjusted Risk Ratio*	95% confidence interval
	DSS	Control		
N (missing)			x.xx	x.xx to x.xx
n (%)				

*adjusted for country, site type (secondary/ tertiary care/mix of both) and study site

Table 28: Effect of DSS on proportion of patients receiving escalated LLT monotherapy

Patients receiving escalated LLT monotherapy	Trial arm		Adjusted Risk Ratio*	95% confidence interval
	DSS	Control		
N (missing)			x.xx	x.xx to x.xx
n (%)				

*adjusted for country, site type (secondary/ tertiary care/mix of both) and study site

Table 29: Effect of DSS on proportion of patients receiving escalated LLT combination therapy

Patients receiving escalated LLT combination therapy	Trial arm		Adjusted Risk Ratio*	95% confidence interval
	DSS	Control		
N (missing)			x.xx	x.xx to x.xx
n (%)				

*adjusted for country, site type (secondary/ tertiary care/mix of both) and study site

Table 30: Effect of DSS on reaching target LDL-C levels

Patients with target LDL-C levels, <1.4 mmol/L (<55 mg/dL) by week 16	Trial arm		Adjusted Risk Ratio*	95% confidence interval
	DSS	Control		
N (missing)			x.xx	x.xx to x.xx
n (%)				

*adjusted for country, site type (secondary/ tertiary care/mix of both) and study site

12.6.Safety Analysis

Table 31: Adverse Device Effects by trial arm

	DSS arm only	
	No. of patients (%)	No. of events
ADE		
SADE		
USADE		
ASADE		

Table 32: Severity of Adverse Device Effects by trial arm

	DSS arm only	
	No. of patients (%)	No. of events
ADE		
Mild		
Moderate		
Severe		

Table 33: Relatedness of Adverse Device Effects by trial arm

	DSS arm only	
	No. of patients (%)	No. of events
ADE		
Related		
Serious and Related		
Serious, Related and Unanticipated		

Table 34: Type of Adverse Device Effects by trial arm

	DSS arm only	
	No. of patients (%)	No. of events
System Organ Class		
Preferred Term		
.....		

12.7.Subgroup Analysis

Forest plots will be presented for subgroup of interested listed in Section 8.8.

12.8.Exploratory Analysis

Table 35: Exploratory endpoints by Week 16 (all patients)

Endpoint	Trial arm		
	DSS	Control	Overall
Patients achieving target LDL-C level <1.8 mmol/L (<70 mg/dL) by Week 16			
N (missing)			
n (%)			
Patients on combination therapies with three oral LLT or 1 injectable therapy plus one or more oral LLT			
N (missing)			
n (%)			
Mortality before Week 16			
N (missing)			
All-cause, n (%)			
Cardiovascular cause , n (%)			
Cardiovascular outcomes occurring during follow up (i.e. after baseline and before Week 16)			
N (missing)			
Coronary artery disease outcome, n (%)			
Myocardial infarction, n (%)			
Coronary Artery Bypass Graft, n (%)			
Angioplasty, n (%)			
Cerebrovascular disease, n (%)			
Aneurysms, n(%)			
Stroke/TIA, n (%)			
Vascular malformations, n (%)			
Carotid stenosis, n (%)			
Peripheral artery disease, n (%)			
Arteriosclerosis obliterans, n (%)			
Arterial insufficiency of the legs, n (%)			
Claudification, n (%)			
Abdominal aortic aneurysm, n (%)			

Imperial Clinical Trials Unit	ZODIAC STATISTICAL ANALYSIS PLAN – MAIN ANALYSIS	V1 17 th Jan 2024
-------------------------------	--	------------------------------

Table 36: LDL-C lowering in LLT-naïve patients by Week 16

Endpoint	Trial arm		
	DSS	Control	Overall
Patients achieving a decrease of baseline in LDL-C level of more than 50% by Week 16			
N (missing)			
n (%)			

Table 37: Percentage change in lipid profile in LLT-naïve patients by Week 16

Endpoint	Trial arm		
	DSS	Control	Overall
Percent change from baseline in LDL-C by Week 16			
N (missing)			
Mean (SD)			
Median (SD)			
Percent change from baseline in HDL-C by Week 16			
N (missing)			
Mean (SD)			
Median (SD)			
Percent change from baseline in non-HDL-C by Week 16			
N (missing)			
Mean (SD)			
Median (SD)			
Percent change from baseline in triglycerides by Week 16			
N (missing)			
Mean (SD)			
Median (SD)			
Percent change from baseline in total cholesterol by Week 16			
N (missing)			
Mean (SD)			
Median (SD)			

Table 38: LDL-C lowering in LLT-naïve patients receiving combination therapy (for at least 4 weeks) by Week 16

Endpoint	Trial arm		
	DSS	Control	Overall
Patients achieving target LDL-C level <1.4 mmol/L (<55 mg/dL) and a decrease of baseline in LDL-C level of at least 50% by Week 16			
N (missing)			
All combination therapies, n (%)			
Oral combination therapies only, n (%)			
Oral plus injectable combination therapy, n (%)			

Imperial Clinical Trials Unit	ZODIAC STATISTICAL ANALYSIS PLAN – MAIN ANALYSIS	V1 17 th Jan 2024
-------------------------------	--	------------------------------

Table 39: LDL-C levels by Week 16 according to LLT therapy at baseline in DSS arm

Endpoint	LLT therapy at baseline		
	None	Monotherapy	Combination
LDL-C level			
N (missing)			
Mean (SD)			
Median (SD)			

Table 40: LDL-C goal achievement (LDL-C < 1.4mmol/L or 55mg/dl)by Week 16 by site type

Site type	Trial arm		
	DSS	Control	Overall
Secondary			
N (missing)			
n (%)			
Tertiary			
N (missing)			
n (%)			
Mixed			
N (missing)			
n (%)			

Table 41: LDL-C goal achievement (LDL-C < 1.4mmol/L or 55mg/dl)by Week 16 by country

Country	Trial arm		
	DSS	Control	Overall
UK			
N (missing)			
n (%)			
Italy			
N (missing)			
n (%)			
Spain			
N (missing)			
n (%)			

Table 42: LDL-C goal achievement (LDL-C < 1.4mmol/L or 55mg/dl) by Week 16 by CV event history

≥1 CV event in 2 years prior to admission	Trial arm		
	DSS	Control	Overall
Yes			
N (missing)			
n (%)			
No			
N (missing)			
Mean (SD)			

Table 43: Qualitative evaluation of DSS

Statement	Rating, mean (SD, range) ^a	Agreement with statement, n (%)	Disagreement with statement, n (%)
1. I think that I would like to use this tool frequently.			
2. I found the tool unnecessarily complex.			
3. I thought the tool was easy to use.			
4. I think that I would need the support of a technical person to be able to use this tool.			
5. I found the various functions in the tool were well integrated.			
6. I thought there was too much inconsistency in this tool.			
7. I imagine that most people would learn to use this tool very quickly.			
8. I found the tool very awkward to use.			
9. I felt very confident using the tool.			
10. I needed to learn a lot of things before I could get going with this tool.			
Statement	Rating, mean (SD, range) ^b	Poor or worse, n(%)	Good or better, n (%)
11. Overall, I would rate the user-friendliness of this tool as			

^a Score from 1 to 5 ^b Score from 1 to 6

Table 44: Qualitative evaluation of DSS – Standardised overall usability score (computed from Questions 1 to 10)

	Overall Usability Score (ranging from 0 to 100)
N (n missing)	
Mean (SD, range)	
Median (IQR)	

12.10. Sensitivity Analysis

Table 45: Effect of DSS on proportion of patients initiated on LLT combination therapy, escalation of LLT monotherapy or escalation of LLT combination therapy in patients with complete outcome data

Patients with primary outcome at 16 weeks	Trial arm		Adjusted Risk Ratio*	95% confidence interval
	DSS	Control		
N (missing)			x.xx	x.xx to x.xx
n (%)				

*adjusted for country, site type (secondary/ tertiary care/mix of both) and study site

Table 46: Effect of DSS on proportion of patients initiated on LLT combination therapy, escalation of LLT monotherapy or escalation of LLT combination therapy inclusive of patients who died (full ITT)

Patients with primary outcome at 16 weeks	Trial arm		Adjusted Risk Ratio*	95% confidence interval
	DSS	Control		
N (missing)			x.xx	x.xx to x.xx
n (%)				

*adjusted for country, site type (secondary/ tertiary care/mix of both) and study site

Imperial Clinical Trials Unit	ZODIAC STATISTICAL ANALYSIS PLAN – MAIN ANALYSIS	V1 17 th Jan 2024
----------------------------------	--	------------------------------

13. Appendix C: Figures to Present

A CONSORT diagram will be used to summarise participant flow as appropriate for cluster trials.

Bar charts with 95% confidence intervals will be used to present proportions of patients meeting the primary outcome and secondary binary outcomes.

Kaplan-Meier plots will be presented for time to event outcomes (i.e. time to intensification of LLT).

Forest plots of adjusted risk ratios will be used to summarise the primary outcome and subgroup analyses described in Section 8.8.

14. Appendix D: Example Code for analysis

14.1. Primary Outcome

```
// Load the data
use "datafile.dta", clear

// Set the maximum number of iterations
set maxiter 1000

// Fit the mixed log-binomial regression model
glm outcome intervention country site_type, family(binomial) link(log) vce(cluster site)
robust

// Display the results
estimates table
```

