6.1. Primary Estimand

In randomised trials there can be post-randomisation events that may have an impact on the outcome and thus the estimation of the effect of the intervention may be ambiguous if we do not consider these events. Therefore, we use the ICH E9 (R1) addendum on estimands and sensitivity analysis¹³ to define the primary estimand with its five attributes: treatment, population, variable, population-level summary, and handling intercurrent events.

The primary objective of the trial is to compare implementation of a DSS added to routine clinical care as compared with routine care without a DSS, to assess whether the availability of a DSS system in current practice increases the likelihood of initiation of combination therapy or escalation of LLT over a 16-week period. This is a pragmatic clinical trial and the primary estimand will be a treatment policy estimand that will answer the question whether DSS added to routine clinical care increases the likelihood of initiation of combination therapy or escalation of LLT over a 16-week period compared with routine care regardless of whether the prescriber uses the DSS for decision making.

The following attributes can describe the primary estimand (**Error! Reference source not found.**):

Imperial Clinical Trials Unit	ZODIAC STATISTICAL ANALYSIS PLAN – MAIN ANALYSIS	V1 17 th Jan 2024
-------------------------------	--	------------------------------

Table 5: Primary estimand attributes for the primary outcome

Estimand Attributes	Definition
Population	Adults admitted with ACS to hospital sites where subsequent study data follow up of the patients is carried out defined by ZODIAC inclusion and exclusion criteria
Treatment conditions	Experimental (DSS and SoC) versus control (SoC alone)
Outcome variables	Patients treated with combination therapy, or who receive escalated monotherapy, or escalated combination therapy, within 16 weeks of the index ACS (regardless of adherence i.e. use of the DSS by the prescribing physician for decision making)
Intercurrent events (and strategies to handle them)	Adherence to the DSS system (at participant level i.e. physician in DSS site does not use DSS) – treatment policy ¹ Patients who die are excluded from the analysis – principal stratum ²
Population Summary measure	Risk ratio adjusted for stratification variables (country and type of site)

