8.4. Primary Efficacy Analysis

The primary outcome measure, the proportion of patients treated with combination therapy, or who receive escalated monotherapy, or escalated combination therapy, within 16 weeks of the index ACS (regardless of adherence at 16 weeks) will be modelled using a generalised linear mixed model. This model will use a binomial distribution, log link function and with fixed effect for country and site type (secondary/tertiary care/mixed) and a random effect for study site (as a random intercept). If there is a convergence problem with the log-binomial model, Poisson regression with robust standard errors (modified Poisson regression) will be used. The intervention effect will be reported as a Risk Ratio with a 95% confidence interval. For primary analysis hypotheses will be tested as two-sided with a significance level of 0.05.

$$\log(\pi_{ij}) = \beta_0 + \beta_1 ACSDSS_{ij} + \beta_2 COUNTRY1_{ij} + \beta_3 COUNTRY2_{ij} + \beta_4 Site\ type_{ij} + \beta_5 Site\ type_{ij} + U_j$$

Where:

Imperial Clinical Trials Unit	ZODIAC STATISTICAL ANALYSIS PLAN – MAIN ANALYSIS	V1 17 th Jan 2024
-------------------------------	--	------------------------------

- π_{ij} : probability of combination therapy for the i^{th} patient in j^{th} site
- $ACSDSS_{ij}$: dummy variable for intervention ($ACSDSS_{ij} = 0$ or 1) for patient i in j^{th} site
- $COUNTRY1_{ij}, COUNTRY2_{ij}$: dummy variable for COUNTRY ($COUNTRY_{ij} = 0$ or 1) for patient i in j^{th} site
- $Site\ type1_{ij}, Site\ type2_{ij}$: dummy variable for Site Type ($Site\ type_{ij} = 0$ or 1) for patient i in j^{th} site type
- U_j : random effect for site $j \sim N(0, \sigma_u^2)$

This model will use the modified intention-to-treat population and will include all eligible and randomised patients through use of multi-level multiple imputation. If any participants die within 16 weeks they will be excluded from this primary analysis and any similar secondary outcome analysis but will be included in the time to event outcomes (until censored). We will tabulate mortality by intervention arm.

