8.5.3. Binary outcomes

- Proportion of patients' reaching target LDL-C levels, <1.4 mmol/L (<55 mg/dL) by Week 16, proportion of patients who receive combination therapy, proportion of patients who receive escalated monotherapy and proportion of patients who receive escalated combination therapy

This analysis will be for all people with Week 16 follow-up.

We will follow the same approach as described for primary outcome and use log-binomial model or modified Poisson regression with a fixed effect for country and site type (secondary/ tertiary care/mix of both) and a random effect for study site (as a random intercept) to estimate an adjusted Risk Ratio with a 95% confidence interval and p-value.

Imperial Clinical Trials Unit	ZODIAC STATISTICAL ANALYSIS PLAN – MAIN ANALYSIS	V1 17 th Jan 2024
-------------------------------	--	------------------------------

Model assumptions for all models will be examined using residual analysis. Following the recommendations by Parker¹⁶ and Rubin¹⁷ no adjustments for multiple testing will be used but a precise, focused interpretation of the individual results for secondary outcomes will be reported.

$$\log(\pi_{ij}) = \beta_0 + \beta_1 ACSDSS_{ij} + \beta_2 COUNTRY1_{ij} + \beta_3 COUNTRY2_{ij} + \beta_4 Site\ type_{ij} + \beta_5 Site\ type_{ij} + U_j$$

Where:

- π_{ij} : probability of combination therapy (or other binary outcome) for the i^{th} patient in j^{th} site
- $ACSDSS_{ij}$: dummy variable for intervention ($ACSDSS_{ij} = 0$ or 1) for patient i in j^{th} site
- $COUNTRY1_{ij}, COUNTRY2_{ij}$: dummy variable for COUNTRY ($COUNTRY_{ij} = 0$ or 1) for patient i in j^{th} site
- $Site\ type1_{ij}, Site\ type2_{ij}$: dummy variable for Site Type ($Site\ type_{ij} = 0$ or 1) for patient i in j^{th} site type
- U_j : random effect for site $j \sim N(0, \sigma_u^2)$

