14.2.2. Continuous outcomes

```
// Load the data
use "datafile.dta", clear

// Fit the mixed multi-level regression model
xtmixed outcome intervention country site_type baseline || site : , covariance(unstructured)

// Display the results
estimates table
```

Imperial Clinical Trials Unit	ZODIAC STATISTICAL ANALYSIS PLAN – MAIN ANALYSIS	V1 17 th Jan 2024
----------------------------------	--	------------------------------

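### SAP section 8.4 specifies a log-binomial model with a site random intercept, but the Appendix D code fits a marginal glm with no random effect, so the primary estimator is not fixed

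*SAP*

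**What the plan says.** **Text.** SAP section 8.4 describes a generalised linear mixed model: binomial, log link, two dummy variables each for country and site type, and "a random effect for study site (as a random intercept"), written as a normal U_j with one variance for all sites. The section ends with a graphical check that this random effect is roughly normal. The fallback is: "If there is a convergence problem with the log-binomial model, Poisson regression with robust standard errors (modified Poisson regression) will be used". That sentence mentions neither site nor clustering.

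**Secondary binary outcomes.** Section 8.5.3 says it follows the primary approach and names a "log-binomial model or modified Poisson regression with a fixed effect for country and site type", with a site random intercept attached.

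**Code.** Section 14.1 gives "glm outcome intervention country site_type, family(binomial) link(log) vce(cluster site"). Section 14.2.3 repeats the command. In both places the comment above it calls the model mixed. For the lipid outcomes, section 14.2.2 writes "xtmixed outcome intervention country site_type baseline || site : , covariance(unstructured"), which does contain a site random effect. Section 14.3, the only code shown for imputed data, fits `lmer` with a random intercept for the cluster.

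**Estimand and table.** Table 5 in section 6.1 asks for a "Risk ratio adjusted for stratification variables (country and type of site"). The footnote to Table 23 in section 12.4.1 says the ratio is also adjusted for study site.

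**The concern.** The text describes a conditional model with a site effect, and the code a marginal model in which site affects only the standard errors. They are different estimators. An analyst could follow either and claim to follow the SAP. The glm is not the Poisson fallback, and it leaves no random effect whose normality could be checked. It is hard to read as shorthand, because the lipid code in the same appendix writes the site effect out.

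The imputation code adds a third model. The primary analysis is to be run on imputed data, yet `lmer` on a binary outcome is a linear model and returns no risk ratio. The primary code also enters country and site type once each without factor notation. If they are stored as numeric codes, each becomes a linear trend rather than the two dummies in the text.

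At stake is the reported effect size, and whether the choice of model is settled before the data are seen. A convergence rule applied separately to each imputed data set could also pool estimates from different models.

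**Working it through.** **1. The plan's own figure.** Inputs from SAP section 4.5: 0.05 versus 0.15, 90% power, two-sided 5%, ICC 0.1, 31 per site.

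- Unclustered size per arm: (1.960 + 1.282)² × (0.05×0.95 + 0.15×0.85) / 0.10² = 183.9.
- Design effect: 1 + (31 − 1) × 0.1 = 4.
- 183.9 × 4 = 735.5, or 23.7 sites, rounded up to 24; 24 × 31 = 744, as stated.
- Dropout: 744 / 0.95 rounds up to 784 per arm, 1568 in total. 31 / 0.95 rounds up to 33 per site, so 33 × 24 = 792 per arm and 1584 in total, as stated.

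The sample size reproduces. The SAP states no expected risk ratio under either model; 0.15 / 0.05 = 3.0 is the ratio the glm targets.

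**2. When the two models agree.** With a log link and a site effect U of the same distribution in both arms, E[exp(β₀ + β₁ + U)] / E[exp(β₀ + U)] = exp(β₁). The conditional and marginal risk ratios are then equal.

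**3. When they do not.** If the ICC is ρ on the proportion scale, the between-site variance is ρp(1 − p). The squared coefficient of variation is ρ(1 − p)/p, and for log-normal site rates the log-scale variance is ln(1 + ρ(1 − p)/p).

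- p = 0.05, ρ = 0.1: ln(2.900) = 1.065, SD 1.03.
- p = 0.15, ρ = 0.1: ln(1.567) = 0.449, SD 0.67.

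One ICC on the proportion scale therefore implies unequal log-scale variances, which the single variance in 8.4 cannot represent.

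**4. Size.** Large-sample maximum-likelihood risk ratio of the common-variance random-intercept model, by numerical integration with 31 per site and no covariates, against the marginal ratio:

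| Rates and assumed site variation | Random intercept | glm |
|---|---|---|
| 5% vs 15%, common log-scale variance 0.25 to 0.92 | 3.00 | 2.94 to 3.00 (site risks capped at 1) |
| 5% vs 15%, ICC 0.1, beta | 3.63 | 3.00 |
| 5% vs 15%, ICC 0.1, probit-normal | 3.54 | 3.00 |
| 5% vs 15%, ICC 0.1, logit-normal | 3.47 | 3.00 |
| 5% vs 15%, ICC 0.1, log-normal capped at 1 | 3.38 | 3.00 |
| 5% vs 15%, ICC 0.064, beta | 3.29 | 3.00 |
| 5% vs 15%, ICC 0.048, beta | 3.16 | 3.00 |
| 20% vs 30% (assumed), ICC 0.1, beta | 1.55 | 1.50 |
| 40% vs 50% (assumed), ICC 0.1, beta | 1.26 | 1.25 |

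In 300 simulated trials per scenario with 24 sites per arm, the beta case at ICC 0.1 averaged 3.55 versus 3.00. With a common log-scale variance both models averaged 3.05.

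**5. Marginal model with 48 sites.** In simulations under the null (48 sites of 31, ICC 0.1, beta site rates, site-clustered errors, normal reference distribution), the type I error was about 6% to 8% without a small-sample correction.

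**The case against.** The strongest reply is that Appendix D is headed as example code, so section 8.4 governs, and that under 8.4 as written the two models target the same risk ratio. The second part is correct, and it removes any claim that the mismatch alone shifts the effect. The first lowers the weight of the mismatch but does not resolve it: this is the only executable version of the primary analysis, and it fits neither the stated model nor the stated fallback.

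Three stronger readings are tempting, and the documents do not support them.

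- **That the plan's ICC makes the answer 3.6 rather than 3.0.** This needs an ICC of exactly 0.1 on the proportion scale in both arms and beta-distributed site rates. The SAP gives one planning value, chosen as conservative, cites 0.048 to 0.064, and states no site distribution. Section 4.5 also ties the 5% rate to combination therapy, while the primary outcome in section 5.2 counts escalated monotherapy and escalated combination therapy too. Its rates may be higher, and the gap then shrinks. With equal rates and equal ICC in the two arms both models target 1, so the gap concerns effect size and is not a source of false positives.
- **That Table 5 requires a population-averaged ratio, so the random intercept must go.** Table 5 asks for adjustment for the stratification variables and does not say marginal or conditional.
- **That the fallback has a type I error of 33%.** Errors that ignored site would give 2(1 − Φ(1.96/√4)) = 0.33. At ICC 0.048 to 0.064 the design effects are 2.44 and 2.92, and the same formula gives 21% to 25%. But section 8.5.3 attaches a site effect, the Table 23 footnote mentions site, and the code clusters on site. The wording in 8.4 is incomplete; nothing in the SAP calls for unclustered errors.

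**Conclusion.** The inconsistency is certain. The text specifies a random-intercept log-binomial model, the code for the primary and secondary binary outcomes fits a marginal glm, and the imputation code fits a linear mixed model. The SAP's own code does not run its stated primary analysis.

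The numerical consequence is conditional. It is nil if log-scale site variance is equal in both arms. At 5% versus 15% with the ICC holding on the proportion scale in both arms, the random-intercept model gives about 3.4 to 3.6 (ICC 0.1, depending on the site distribution) or 3.2 to 3.3 (ICC 0.048 to 0.064, beta site rates), against 3.0 from the glm. At an assumed 20% versus 30% the difference is about 1.55 versus 1.50. Confidence is high on the mismatch and moderate on its size, because the rates of the composite outcome and the between-site distribution are not given.

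**What to change.** Name one primary model and make sections 8.4, 8.5.3 and Appendix D (14.1, 14.2.3 and 14.3) agree, with country and site type entered as factors. Either option is defensible:

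- **Keep the random-intercept log model.** Code it as such, and standardise its predictions to a population risk ratio.
- **Use a marginal log-link model.** Cluster the errors on site and add a small-sample correction for 48 sites. Remove U_j and its normality check from the text.

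Under either option, state in 8.4 that the modified Poisson fallback accounts for site by clustering. Replace the linear `lmer` step in 14.3 with the chosen model, and fit the same model in every imputed data set, so that a convergence failure in one does not mix estimators.

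The cost is minor editing of the SAP and code, plus slightly wider intervals from the small-sample correction if the marginal model is chosen.
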